3.0	05 Apr 2018	
Corrected error in the flow diagram – number of subjects changed from N=50 to N=70; pilot cohort corrected to randomized cohortRemoved 'stenosed' in the study objective and design sections
4.0	26 Apr 2018	
Increased the number of enrolling sites for the PK cohort to up to 3 study centers and indicated PK enrollment firstUpdated study population to include only patients who had prior endoscopic sinus surgery (> 30 days with a healed mucosa), including ethmoidectomy and uncinatectomyEdited inclusionary criteria to disallow any additional surgical interventions at the baseline balloon dilation procedureEdited exclusionary criteria to disallow patients with cystic fibrosisIncluded assessment of urinary cortisol over 24 hours at baseline (pre-procedure) and 24 hours after the baseline procedure (post-procedure) towards additional safety assessment in the PK cohortIncluded descriptive statistics for analysis of safety measures

		
• Updated concomitant medications in the synopsis to match the body of the protocol• Updated flow diagram and schedule of assessments table for PK cohort to include urine analysis at baseline and Day 1 post-procedure; separated screening and baseline visits• Deleted reference to investigator brochure for site training (Section 17.2.1)
5.0	21 June 2018	
• Added Day 60 follow-up visit to the Randomized cohort and updated relevant sections throughout the protocol to include Day 60 visit• Updated Day 30 visit window from \pm 3 days to \pm 2 days in the Randomized cohort• Modified inclusionary criteria to allow CT scan confirming bilateral frontal disease within 30 days prior to randomization in the Randomized cohort instead of 30 days prior to enrollment• Updated compatible accessory devices and baseline procedure steps to include an optional use of sinus guide catheter handle• Updated baseline procedure steps to align with the IFU• Removed IFU as an appendix to the ASCEND protocol• Updated reference to “guidewire” to “lightwire” throughout protocol• Updated baseline procedure description to allow for dilation of the maxillary and/or sphenoid sinus, if clinical necessary in the Randomized cohort, with a commercially available balloon sinuplasty device prior to randomization
6.0	22 October 2018	
• Updated the name of the investigational device to UP Drug-Coated Device and the name of the control device to the ‘UP Control Device’• Changed the timepoint of the primary efficacy endpoint in the randomized cohort from Day 30 to Day 14• Added video-endoscopy grading by an independent reviewer at Day 14• Updated exclusion criteria (a) to exclude patients with ethmoid polyposis of grade ≥ 2• Removed the assessment of estimated FSO diameter post-dilation following the baseline procedure• Added a 14-day restriction for use of oral steroids, budesonide or other steroid irrigations/rinses or drops, and nebulized

		
steroids administered nasally, prior to the baseline procedure in the randomized cohort
 
• Updated required use of saline sprays/rinses/irrigations starting on Day 2 in all subjects in the randomized cohort• Updated allowance of intranasal corticosteroid sprays after Day 14 if medically necessary in the randomized cohort• Updated Day 60 visit window from \pm 3 days to \pm 7 days in the randomized cohort• Modified inclusion criteria (f) to allow dilation of the maxillary and/or sphenoid sinus with a commercially available sinus dilation device, if clinically necessary, prior to randomization in the randomized cohort.• Modified inclusion criteria (k) to include optional use of a frontal sinus seeker to assess feasibility of balloon dilation of the FSO• Added a section to describe the personnel and measures to achieve blinding in the randomized cohort• Increased the number of enrolling sites for the randomized cohort to up to 12 study centers
7.0	12 November 2018	
• Changed the timepoint of the primary efficacy endpoint in the randomized cohort from Day 14 to Day 30• Added definition of acute rhinosinusitis to Section 3: Definition of terms• Clarified the use of corticosteroid-eluting implants (including PROPEL[®], PROPEL[®] Mini, PROPEL[®] Contour and SINUVA[®] Sinus Implant) is prohibited 14 days prior to baseline

2 LIST OF ABBREVIATIONS

Abbreviations	Expansion
ADE	adverse device effect
AE	adverse event
AERD	aspirin exacerbated respiratory disease
ARS	acute rhinosinusitis
ASADE	anticipated serious adverse device effect
BSD	balloon sinus dilation
CFR	Code of Federal Regulations
CI	confidence interval
COPD	chronic obstructive pulmonary disease
CRA	clinical research associate
CRF	case report form
CRS	chronic rhinosinusitis
CSF	cerebrospinal fluid
CSR	clinical study report
CT	computed tomography
EDC	electronic data capture
e.g.	'exempli gratia' in Latin, meaning 'for example'
ESS	endoscopic sinus surgery
et al	'et alia' in Latin, meaning 'and others'
FDA	Food and Drug Administration
FSO	frontal sinus ostium/ostia
GCP	good clinical practice
HIV	human immunodeficiency virus
ICF	informed consent form
ICH	International Council on Harmonisation
i.e.	'id est' in Latin, meaning 'that is'
IFU	instructions for use
INCS	intranasal corticosteroids
IRB	institutional review board
ITT	intent-to-treat
IUD	intrauterine device
IV	intravenous
LLOQ	lower limit of quantification
MF	mometasone furoate
PTE	per-treatment-evaluable
RESS	repeat endoscopic sinus surgery
SAE	serious adverse event
SADE	serious adverse device effect
SNOT-22	Sino-Nasal Outcome Test
UADE	unanticipated adverse device effect
USADE	unanticipated serious adverse device effect

3 DEFINITIONS OF TERMS

Term	Definition
Adverse device effect (ADE)	Adverse event related to the use of an investigational medical device. This definition includes adverse events resulting from insufficient or inadequate instructions for use, deployment, implantation, installation, or operation, or any malfunction of the investigational medical device. This definition includes any event resulting from use error or from intentional misuse of the investigational medical device. [BS EN ISO 14155]
Adverse event (AE)	Any untoward medical occurrence, unintended disease or injury, or untoward clinical signs (including abnormal laboratory findings) in subjects, users or other persons, whether or not related to the investigational medical device [BS EN ISO 14155]
Adhesion/scarring grading scale for the ethmoid sinus	Adhesion/scarring severity in the ethmoid sinus graded on a 5-point scale from 0 to 4 at the screening and baseline visits, as follows: 0: None 1: Small but non-obstructing (no separation required) 2: Obstructing, but easily separated 3: Dense and obstructing, separation difficult 4: Severe: complete adhesion of the middle turbinate to the lateral nasal wall
Adhesion/scarring grading scale for the FSO	Adhesion/scarring in the frontal sinus ostium/ostia (FSO) assessed on a 4-point scale as follows: 0: No visible granulation/scarring in the FSO 1: Minimal amount of granulation, scarring or contraction observed but not obstructing the FSO (intervention not warranted) 2: Moderate amount of obstructive granulation, scarring or contraction present in the FSO (intervention is warranted) 3: Significant amount of scarring or contraction causing obstruction of the FSO requiring intervention (likely to compromise patency if not removed)
Acute rhinosinusitis (ARS)	Per the 2016 “International Consensus Statement on Allergy and Rhinology” definition, patient must have \leq 4 weeks of symptomatic inflammation of the paranasal sinuses and nasal cavity.
Aspirin exacerbated respiratory disease (AERD)	Aspirin exacerbated respiratory disease, also known as Samter’s Triad, is a chronic medical condition that consists of three clinical features: asthma, sinus disease with recurrent nasal polyps, and sensitivity to aspirin and other non-steroidal anti-inflammatory drugs.
Case report form (CRF)	Standardized forms designed to capture study data as required by the protocol.
Chronic rhinosinusitis (CRS)	Per the 2016 “International Consensus Statement on Allergy and Rhinology” definition, patient must have \geq 12 weeks of: 
• Two or more of the following symptoms:
○ Nasal discharge (anterior/posterior)○ Nasal blockage/obstruction/congestion

Term	Definition
	
 ○ Reduction/loss of smell ○ Facial pressure/pain ● And one or more of the following findings: 
 ○ Evidence of inflammation on paranasal sinus examination or computed tomography ○ Evidence of purulence coming from paranasal sinuses or ostiomeatal complex
Device malfunction	
Investigational device: Failure to perform in accordance with its intended purpose when used in accordance with the instructions for use or clinical investigation plan. [BS EN ISO 14155]
 
Compatible accessory devices: Failure to meet its performance specifications or otherwise perform as intended. Performance specifications include all claims made in the labeling for the device. The intended performance of a device refers to the intended use for which the device is labeled or marketed. [21 CFR 803]

Enrolled	Subjects are considered enrolled upon signing the informed consent form.
Estimated FSO diameter	Smallest and largest diameters of the FSO are estimated endoscopically by probing with a 3-mm olive-shaped frontal sinus suction tip and reported in mm.
Inflammation score	For the purpose of the endoscopic scoring method in this study, the term inflammation is a global descriptor defined to include mucosal edema, erythema hypertrophy and/or polypoid changes. The inflammation present in the frontal recess/FSO is estimated visually based on the endoscopic examination on a scale ranging from 0 (no visible inflammation) to 100 (severe inflammation) involving extensive erythema, edema, or polyposis.
Intent-to-treat population	Consists of all subjects in whom a sinus dilation was attempted. An attempt occurs when the physician introduces the delivery system into the subject's nostril with the intent of dilation.
Patency grading scale for the FSO	
Patency of the FSO assessed endoscopically by probing with a 3-mm olive-shaped frontal sinus suction tip ("suction tip") and graded on a 5-point scale as follows:
 
 0: Occluded (no opening visible) 1: Significantly stenosed (not occluded, but unable to pass the 3-mm suction tip) 2: Moderately stenosed (able to easily pass the 3-mm suction tip with no additional space around it) 3: Minimally stenosed (able to easily pass the 3-mm suction tip with additional 1-2 mm space around it) 4: Completely patent (able to easily pass the 3-mm suction tip with additional > 2 mm space around it)
Per-treatment-evaluable (PTE) population	Consists of all randomized patients who have received the assigned study device in the target sinus, who have no major procedural protocol deviations and for whom follow-up data are available.

Term	Definition
Polyp grading scale for the ethmoid sinus	
Polyps originating from the ethmoid sinus assessed endoscopically and graded on an 8-point scale ranging from 0 to 4 as follows:
 
 0: No visible sinonal polyps 1: Small amount of sinonal polyps confined in middle meatus 1.5: Small amount of sinonal polyps confined in middle meatus with expanded amount of polypoid edema obstructing $\geq 25\%$ of the ethmoid sinus cavity 2: Expanded amount of sinonal polyps confined in middle meatus 2.5: Expanded amount of sinonal polyps confined in middle meatus with expanded amount of polypoid edema obstructing $\geq 50\%$ of the ethmoid sinus cavity 3: Sinonal polyps extending beyond middle meatus but not totally obstructing the nasal cavity 3.5: Sinonal polyps extending beyond middle meatus with expanded amount of polypoid edema obstructing $\geq 75\%$ of the ethmoid sinus cavity 4: Sinonal polyps completely obstructing the nasal cavity
Polypoid edema grading scale for the FSO	
Polypoid edema in the frontal recess/FSO is assessed on a 4-point scale as follows:
 
 0: Normal mucosa, no visible polyps/mucosal edema 1: Minimal amount of polyps/mucosal edema 2: Moderate amount of polyps/polypoid edema 3: Expanded amount of polyps/polypoid edema
Safety population	
Consists of all subjects exposed to investigational device with successful dilation of at least one FSO

Serious adverse event (SAE)	
Adverse events are considered “serious” if, in the view of either the investigator or sponsor, they result in any of the following outcomes:
 
 • Death; or • A life-threatening illness or injury; or • Permanent impairment of a body structure or a body function; or • Inpatient hospitalization or prolongation of existing hospitalization; or • Medical or surgical intervention to prevent life-threatening illness or injury or permanent impairment to a body structure or a body function; or • Fetal distress, fetal death, or a congenital anomaly/birth defect. 
Important medical events that may not result in death, be life-threatening, or require hospitalization may be considered serious when, based upon appropriate medical judgment, they may jeopardize the patient and may require medical or surgical intervention to prevent one of the outcomes listed in this definition. [BS EN ISO 14155]

Serious adverse device effect (SADE)	
Adverse device effect that has resulted in any of the consequences characteristic of a serious adverse event. Anticipated serious adverse

Term	Definition
	device effect (ASADE) is an effect which by its nature, incidence, severity or outcome has been identified in the risk analysis report.
Sino-Nasal Outcome Test (SNOT-22)	Validated, disease-specific, symptom-scoring instrument consisting of 22 questions, each scored by patient on a 6-point scale as follows: 0: No problem 1: Very mild problem 2: Mild or slight problem 3: Moderate problem 4: Severe problem 5: Problem as bad as it can be The maximum total score for all symptoms is equal to 110.
Source data	All information in original records and certified copies of original records of clinical findings, observations, or other activities in a clinical trial necessary for the reconstruction and evaluation of the trial.
Source documents	Original documents, data, and records. Printed, optical, or electronic documents containing source data.
Subject	An individual who participates in a clinical investigation.
Successful dilation of the FSO	Insertion of the UP Device into the targeted FSO followed by 2 consecutive complete inflations of the balloon.
Unanticipated adverse device effect (UADE)	Any serious adverse effect on health or safety or any life-threatening problem or death caused by, or associated with, a device, if that effect, problem, or death was not previously identified in nature, severity, or degree of incidence in the investigational plan or application, or any other unanticipated serious problem associated with a device that relates to the rights, safety, or welfare of subjects. [21 CFR 812]
Unanticipated serious adverse device effect (USADE)	Any serious adverse device effect which by its nature, incidence, severity or outcome has not been identified in the current version of the risk analysis report. [BS EN ISO 14155; 21 CFR 812]
Use error	Act or omission of an act that results in a different medical device response than intended by the manufacturer or expected by the user NOTE: Use error includes slips, lapses, and mistakes. An unexpected physiological response of the subject does not in itself constitute a use error. [BS EN ISO 14155]

4 PROTOCOL SUMMARY

Study Title	The ASCEND Study: A Clinical Evaluation of the UP Drug-Coated Device in Patients with Chronic Rhinosinusitis
Objective	To assess the safety, performance, and efficacy of the UP Drug-Coated Device when used in chronic rhinosinusitis (CRS) patients undergoing balloon dilation of frontal sinus ostia (FSO)
Investigational Device	UP Drug-Coated Device (mometasone furoate, 3000 mcg) and UP Control Device (together referred to as “UP Device”) are balloon dilation devices intended to dilate the peripheral sinus ostia. The UP Drug-Coated Device is intended to dilate and locally deliver steroids to the frontal sinus ostia to maintain patency in patients ≥ 18 years of age.
Study Design	Prospective, multicenter, clinical trial enrolling and treating a total of 75 subjects in two cohorts: 
• PK cohort (N=5): A non-randomized cohort to assess the systemic safety and performance of the UP Drug-Coated Device for in-office bilateral dilation of the FSO (2 inflations in each FSO for a total of 4 inflations per device). Subsequently, the UP Drug-Coated Device may be used to dilate any sphenoid or maxillary sinuses.• Randomized cohort (N=70): A randomized, intra-patient controlled, blinded cohort of 70 subjects to assess the safety and efficacy of the UP Drug-Coated Device used for in-office dilation of the FSO. The FSO randomized to the treatment (Treatment) will undergo dilation using the UP Drug-Coated Device (2 inflations per device) while the contralateral FSO (Control) will be dilated with a UP Control Device (2 inflations per device).
Subject Enrollment	PK cohort : 5 subjects at up to 3 study centers. Randomized cohort : 70 subjects at up to 15 study centers across the U.S. The PK cohort will enroll first.
Study Population	Patients ≥ 18 years of age with chronic rhinosinusitis (CRS) who had prior endoscopic sinus surgery (ESS) including ethmoidectomy and uncinatectomy and are candidates for balloon dilation because they present with bilateral stenosis of the frontal recess/FSO due to scarring or polypoid edema, confirmed on endoscopy.
Eligibility Criteria	Key inclusion criteria: 
• Confirmed diagnosis of CRS per the 2016, “International Consensus Statement on Allergy and Rhinology” definition. Patient must have ≥ 12 weeks of:
○ Two or more of the following symptoms:
■ nasal discharge (anterior/posterior)■ nasal blockage/obstruction/congestion

[figure not shown]
	
▪ reduction/loss sense of smell▪ Facial pressure/pain○ And one or more of the following findings:
▪ Evidence of inflammation on paranasal sinus examination or computed tomography (CT)▪ Evidence of purulence coming from paranasal sinuses or ostiomeatal complex• Bilateral disease in the frontal sinuses (Lund-Mackay score ≥ 1 on each side) on CT scan within 30 days prior to enrollment in the PK cohort and prior to randomization in the randomized cohort.• Patient has bilateral obstruction of the frontal recess/FSO due to scarring and/or polypoid edema confirmed on endoscopy (patency grade of 0 or 1 for each FSO).• Balloon dilation of the FSO judged to be feasible (use light-assisted or image-guided instrument such as a frontal sinus seeker tip to confirm access of each FSO) and medically appropriate.• Patient has had prior ESS (> 30 days with a healed mucosa) including bilateral ethmoidectomy (anterior or total) and uncinatectomy for better visualization of the FSO. Note: No additional surgical interventions will be allowed at baseline/procedure. Dilation of the maxillary and/or sphenoid sinus can be performed with a commercially available sinus dilation device, if clinically necessary, prior to randomization in the randomized cohort.
Primary Endpoints	PK cohort: Successful dilation of attempted FSO using the UP Drug-Coated Device with no unanticipated serious adverse device effects (USADE)

	
Randomized cohort: Difference in the patency grade of the FSO between treatment sides at Day 30, as determined by an independent, blinded sinus surgeon based on the centralized video-endoscopy review

Secondary Endpoints	
Endoscopic endpoints in the FSO by clinical investigators at specified timepoints through Day 30 in the PK cohort and through Day 60 in the randomized cohort:
 
• Estimated diameter, smallest and largest (mm)• Frequency and grade of patency (5-point categorical scale)• Inflammation (0-100 scale)• Frequency and severity of adhesion/scarring (4-point categorical scale)• Frequency and grade of polypoid edema (4-point categorical scale)• Need for and frequency of post-dilation interventions (e.g., medical, repeat dilation, surgical) 
Endoscopic endpoints in the FSO by independent reviewer in the randomized cohort:
 
• Estimated diameter, smallest and largest (mm) at Day 14 and Day 30• Frequency and grade of patency at Day 14 and frequency of patency at Day 30 (5-point categorical scale)• Inflammation (0-100 scale) at Day 14 and Day 30• Frequency and severity of adhesion/scarring (4-point categorical scale) at Day 14 and Day 30• Frequency and grade of polypoid edema (4-point categorical scale) at Day 14 and Day 30• Need for and frequency of post-dilation interventions (e.g., medical, repeat dilation, surgical) at Day 14 and Day 30 
Patient-reported outcomes (PK cohort only):
 
• Change from baseline to Day 14 and Day 30 in Sino-Nasal Outcome Test (SNOT-22) scores
Safety Evaluation	
PK cohort:
 
• Measurement of plasma concentrations of MF and cortisol at baseline before the baseline procedure (dilation) and at 0.5, 1, 2, 4, and 24 hours after dilation, and again in the morning of Days 3, 7, 14 and 30
◦ A validated bioanalytical method for human plasma MF with a lower limit of quantification (LLOQ) of 0.25 pg/mL◦ A validated bioanalytical method for cortisol with a LLOQ of 1.00 ng/mL• Measurement of urinary cortisol excretion for 24 hours prior to the baseline procedure and for 24 hours after the baseline procedure
◦ A validated bioanalytical method for human urinary cortisol with a LLOQ of 1.00 ng/mL

	
All adverse events reported by subjects between enrollment and Day 30 (end of study) will be tabulated.
 
Randomized cohort: All adverse events reported by subjects between enrollment and Day 60 (end of study) will be tabulated.

Concomitant Medications	
Leading up to the baseline procedure, there is a 30-day restriction for use of parenteral and injected steroids (e.g., Kenalog).Leading up to the baseline procedure, a 14-day restriction for use of oral steroids, budesonide or other sinus steroid irrigations/rinses or drops, nebulized steroids administered nasally.After the baseline procedure, subjects will be allowed in the PK cohort and required in the randomized cohort to use saline sprays/rinses/irrigations starting from Day 2.If infection is suspected at any time during the study, treatment with antibiotics will be permitted.Use of intranasal corticosteroid (INCS) sprays will be allowed starting after Day 14 visit in the randomized cohort, if medically necessary, and not allowed throughout the 30-day follow-up duration in the PK cohort.Use of other corticosteroids (e.g., oral, parenteral, injections, budesonide or other sinus steroid irrigations/rinses or drops, breath powered steroid delivery [e.g. XHANCE™, fluticasone propionate], nebulized steroids administered nasally) will not be permitted during the study follow-up unless clinically necessary.Use of orally-inhaled steroids for control of asthma will be permitted, if already on such medications.Use of corticosteroid-eluting sinus implants (PROPEL®, PROPEL® Mini, PROPEL® Contour, SINUVA® Sinus Implant) or other nasal packing and spacers is prohibited 14 days prior to baseline and during the baseline procedure and through Day 30 in the PK cohort and through Day 60 in the randomized cohort.To the extent possible, subjects will be maintained on stable regimens of leukotriene inhibitors and/or immunotherapy for allergies, if currently on such regimens.
Follow-up	
PK cohort: Each subject will return for 6 follow-up visits at Days 1 (24 hr collection), 3, 7, 14, 21 and 30. All blood draws during follow-up should occur in the morning.
 
Randomized cohort: Each subject will return for 5 follow-up visits at Days 7, 14, 21, 30 and 60.
 
Subjects in both cohorts may come in for additional unscheduled office visits if necessary. Circumstances that may warrant additional visits include but are not limited to: worsening of sinus symptoms, and/or sinus-related adverse events requiring medical evaluation.

Duration of Study Period	For a given subject in the PK cohort: Approximately 32 days = screening visit (1 day) + baseline/procedure (1 day) + follow-up (30 days) For a given subject in the randomized cohort: Approximately 62 days = screening visit (1 day) + baseline/procedure (1 day) + follow-up (60 days) Overall: Approximately 8 months = 6-month enrollment phase + 2-month follow-up.
---------------------------------	---

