8.4 Role of the Independent Reviewer

Video-endoscopies of the FSO at Day 14 and Day 30 from all subjects in the randomized cohort will be provided to an independent sinus surgeon reviewer for grading and determination of the primary and secondary efficacy endpoints. The reviewer will be independent from the study (i.e., not enrolling study subjects for the study) and masked to treatment assignment (i.e., not know which sides received the UP Drug-Coated Device and the UP Control Device). To reference the subjects' pre-dilation anatomy as needed, the independent reviewer will have access to the pre-procedure videos.

Video-endoscopies obtained pre-procedure, at Day 14 and at Day 30 will be labeled with subject ID and will be checked to ensure no subject-identifying information (e.g., images of subjects' face) is included before being provided to the independent reviewer.

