9.4.2 Randomized Cohort

The sample size was calculated based on the difference in the patency grade at Day 30 between the treatment and control sides with the following assumptions:

- Expected mean difference of 0.5 between the treatment and control sides in patency grade
- A SD of 1.1 for side-to-side difference in the patency grade of the FSO
- Target power of $\geq 90\%$
- Type I error rate of $\alpha = 0.05$, 2-sided

A mean difference in patency grade of 0.5 between the treatment and control sides favoring treatment sides was considered clinically meaningful. Based on standard formulas for a paired t-test, a sample size of 53 subjects provides at least 90% power to detect a difference of 0.5 in mean patency grade between treatment sides. Assuming up to 25% of subjects with non-evaluable data on one or both sides, additional 17 subjects will be enrolled for a total of 70 subjects in the randomized cohort.

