10.3.2 Randomized Cohort – Primary Efficacy Endpoint

The primary efficacy endpoint is the difference in patency grade of the FSO between the treatment and control sides at Day 30 as determined by an independent, blinded sinus surgeon based on the centralized video-endoscopy review. Patency of the FSO will be assessed endoscopically by probing with a 3-mm olive-shaped frontal sinus suction tip (“suction tip”) and will be analyzed using the paired t-test.

For each subject, the difference in patency grade of the FSO between the treatment and control sides will be calculated and then averaged across all subjects. The difference in patency grade for a given subject will be set as missing if one of the FSO is unable to be viewed or graded.

The primary efficacy hypothesis is that mometasone furoate (MF) from the UP Drug-Coated Device will significantly increase the patency grade on the treatment side compared to control. The statistical test will be paired t-test where the difference in patency grade between treatment and control sides is determined.

The relevant null and alternative hypotheses for this primary efficacy endpoint are:

- $H_0: \mu = 0$
- $H_1: \mu \neq 0$

where μ is the mean difference in the FSO patency grade between the treatment and control sides at Day 30. The study will be considered successful if there is a statistically significant difference in the mean patency grade in favor of the UP Drug-Coated Device.

Although the alternative hypothesis is specified as two-sided, only a statistically significant difference in patency grade favoring treatment sides will constitute evidence of effectiveness. The two-sided α for this test is 0.05 (or one-sided α of 0.025).

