10.3.2.2 Sensitivity Analyses for Missing Data

Subjects with missed visit, lost to follow-up or patency grade ‘unable to view’ by the independent reviewer will be considered as missing data. If more than 10% of the primary efficacy data are missing, the following imputation analyses will be performed to assess the sensitivity of conclusions to missing data from the independent reviewer:

- Impute ‘4’, for all missing values on the control sides and ‘0’ on the treatment sides; this is a worst-case imputation.
- Impute ‘0’, for all missing values on the control sides and ‘4’ on the treatment sides; this is a best-case imputation.
- A “tipping point” analysis in which all missing observations on the control side will systematically be assigned a 0, 1, 2, 3 or 4, and all missing observations on the treatment side will separately be assigned a 0, 1, 2, 3, or 4, for a total of $5 \times 5 = 25$ analyses.
- Impute patency grades at Day 30 by clinical investigators in subjects missing values on the control or treatment sides.

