10.4.2 Randomized Cohort

10.4.2.1 Endoscopic Outcomes Assessed by Independent Reviewer

Descriptive statistics such as means, SD, median and, where appropriate, 95% CI will be computed for all continuous measures. Paired t-test will be used to assess side-to-side differences between treatment sides.

Descriptive statistics and side-to-side differences between treatment and control sides will be analyzed for the following outcomes:

- Patency grade of the FSO at Day 14
- Polypoid edema grade of the FSO at Day 14 and Day 30
- Estimated largest diameter of the FSO at Day 14 and Day 30
- Inflammation in the frontal recess/FSO at Day 14 and Day 30

Categorical measures will be analyzed as counts, proportions and frequencies and, where appropriate, 95% CI will be computed. Categorical data that can be localized to the treatment or control side will be analyzed using McNemar's test for correlated proportions. An exact version of McNemar's test will be performed for correlated proportions.

Counts, proportions and frequencies and side-to-side differences between treatment sides will be analyzed for the following categorical measures by independent reviewer at Day 14 and Day 30:

- Patency grade: sinuses with clinically significant stenosis/occlusion in the FSO (patency grade 0 or 1).
- Adhesion/scarring grade: sinuses with clinically significant amount of adhesion/scarring in the frontal recess/FSO (adhesion/scarring grade 2 or 3)
- Polypoid edema grade: sinuses with clinically significant amount of polypoid edema in the frontal recess/FSO (polypoid edema grade 2 or 3)

- Need for post-dilation intervention: proportion of sinuses that need post-dilation interventions in the frontal recess/FSO (e.g., steroid, surgical, repeat balloon dilation).

Additional grouping for the above variables will also be analyzed.

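### The Day 30 missing-data plan makes no use of the masked reviewer's Day 14 patency grades; one added repeated-measures model would supply the estimate it lacks

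*Protocol*

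**What the plan says.** **Endpoint and rater.** SAP 10.3.2 defines the primary endpoint as the "difference in patency grade of the FSO between the treatment and control sides at Day 30 as determined by an independent, blinded sinus surgeon".

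**Visits graded.** SAP 8.4 sends the same masked reviewer the "Video-endoscopies of the FSO at Day 14 and Day 30 from all subjects in the randomized cohort". Among the reviewer's secondary endpoints, Protocol section 4 has "Frequency and grade of patency at Day 14 and frequency of patency at Day 30 (5-point categorical scale". SAP 10.4.2.1 analyses the reviewer's Day 14 patency grade only as an outcome in its own right ("Patency grade of the FSO at Day 14").

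**Incomplete pairs.** Under SAP 10.3.2 a subject's difference "will be set as missing if one of the FSO is unable to be viewed or graded". SAP 9.3.2 imputes nothing by default.

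**Missing-data analyses.** SAP 10.3.2.2 counts missed visits, loss to follow-up and unviewable videos as missing. If more than 10% of the primary data are missing, it runs four analyses:
- worst case (control 4, treatment 0);
- best case (the reverse);
- a tipping-point grid of 25 constant fills;
- "Impute patency grades at Day 30 by clinical investigators in subjects missing values on the control or treatment sides".

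**Expected loss.** SAP 9.4.2 sizes the cohort "Assuming up to 25% of subjects with non-evaluable data on one or both sides".

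Protocol 16.7 leaves missing-data sensitivity work to the SAP, so SAP 10.3.2.2 is where any gap has to be closed.

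**The concern.** The reviewer's Day 14 grade is probably the best available predictor of the reviewer's missing Day 30 grade: same masked rater, same ostium, same scale, about 16 days earlier. No Day 30 analysis uses it.

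The complete-pair t-test is unbiased if Day 30 pairs are missing completely at random. If the chance of having a Day 30 pair depends on what was seen at Day 14, the complete-pair mean can be off. Such dependence is plausible, because nasal steroid sprays become available after the Day 14 visit and intervention may follow worsening (Protocol sections 12 and 13).

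The planned checks do not supply a corrected estimate. Three of them use constants. The fourth borrows the investigator's Day 30 grade, which can replace an unviewable video but does not exist after a missed Day 30 visit or loss to follow-up. At stake is a credible central estimate around which the extreme analyses can be read, when the plan itself allows for about a quarter of pairs being lost.

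**Working it through.** **1. The plan's own figures.** SAP 9.4.2 gives a difference of 0.5, SD 1.1 and two-sided alpha 0.05. Exact noncentral-t power for a paired t-test is 89.5% with 52 pairs and 90.1% with 53, so the stated 53 reproduces. Then 53 + 17 = 70, and 17/70 = 24.3% lost. The 10% trigger is 7 of 70, so the four analyses run only when 8 or more pairs are missing.

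**2. What the constant fills give.** Suppose 17 pairs are missing on both sides and the 53 observed pairs average 0.5.
- Worst case: (53 x 0.5 + 17 x (-4))/70 = -0.59.
- Best case: (53 x 0.5 + 17 x 4)/70 = +1.35.
- Grid: each one-grade step in the imputed difference moves the mean by 17/70 = 0.24.

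These figures show fragility. They do not estimate the Day 30 difference.

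**3. Precision from adding Day 14.** Take m = 53 Day 30 pairs, n = 53 plus the number of subjects with a Day 14 pair only, and rho = the correlation of the Day 14 and Day 30 side differences. The documents do not give rho; I assume 0.5-0.8. For bivariate-normal maximum likelihood:

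Var = SD^2 x [(1 - rho^2)/m + rho^2/n], so effective N = 1/[(1 - rho^2)/m + rho^2/n].

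Example, rho = 0.5 and all 17 with Day 14: 0.75/53 + 0.25/70 = 0.01772, giving N = 56.4.

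| rho | Effective N, 17 of 17 have Day 14 | Power | Effective N, 8 of 17 | Power |
|---|---|---|---|---|
| 0.5 | 56.4 | 91.8% | 54.8 | 91.1% |
| 0.7 | 60.2 | 93.4% | 56.6 | 91.9% |
| 0.8 | 62.8 | 94.3% | 57.9 | 92.5% |

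Against 90.1%, the gain is about 1.7-4.2 points at most and about 1-2.4 points if 8 of the 17 have a Day 14 pair. If none has one, Day 14 adds nothing.

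**4. Bias.** I simulated 20,000 trials of 70 subjects with bivariate-normal side differences, SD 1.1 at both visits, 24% of Day 30 pairs missing and a Day 14 pair present for all. The log-odds of missingness change by 1 per 1.1 grades (one SD of the difference). The missingness models are assumptions.

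- *Driven by the absolute Day 14 difference.* At a true difference of 0.50 the complete-pair mean is 0.45 (rho 0.5) and 0.43 (rho 0.7). With no true difference, one-sided rejection stays at about 2.5%.
- *Driven by the signed difference, lost when the treated side compares poorly.* Complete-pair mean 0.57, 0.61, 0.66 at rho 0.3, 0.5, 0.7. With no true difference, one-sided rejection is 6.5%, 11.2%, 18.7% against a nominal 2.5%.
- *Driven by the signed difference, reversed.* Complete-pair mean 0.43, 0.39, 0.34.

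The estimate that uses Day 14 stays at 0.50 in all of these. Its null rejection in the second scenario is 2.6-2.8%.

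**The case against.** The strongest reply is that the design itself limits the harm. Each subject is their own control, devices carry codes, they are not compared side by side, and the reviewer is masked (Protocol 17.3.2, SAP 8.4). A missed visit removes both sides together. Missingness that treats the two sides alike leaves the false-positive rate at its nominal level and can only shrink the effect. A reader might infer from the signed scenario that the planned test has an inflated type I error. The documents do not support that: it needs missingness that tells the treated side from the control side, which masking makes less likely. This part of the reply stands.

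Three further points also stand:
- A reader might infer that the plan is blind to missing-data bias. It is not: the 25-cell grid shows where the conclusion tips, and at the planned loss it would be triggered.
- A reader might infer that Day 14 grades, or single readable Day 30 sides, are thrown away altogether. Day 14 patency is a secondary endpoint, and SAP 10.3.2.2 imputes by side, so a readable Day 30 side can be kept there. The loss is confined to the primary test.
- For an unviewable video, the investigator's grade from the same visit may be closer to the truth than a reviewer grade some 16 days older, particularly if sprays or rescue came in between.

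What remains is narrower. After a missed Day 30 visit or loss to follow-up no investigator grade exists, and no planned analysis then gives an estimate valid under missingness that depends on Day 14.

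**Conclusion.** The concern holds as a cheap improvement to SAP 10.3.2.2. It is not a flaw in the primary test or the sample size: the paired t-test is valid if pairs are missing completely at random, and the 70 already allow for the planned loss.

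The gap is the absence of a missing-at-random estimate that uses data already collected. Its possible size is a shrinkage of about 0.05-0.07 grade under absolute-difference missingness (0.43-0.45 against 0.50; correlation 0.5-0.7). Under signed missingness it is a bias of roughly 0.07-0.16 grade in either direction (correlation 0.3-0.7), set against a planned effect of 0.5. The precision gain is secondary.

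All of this rests on an assumed correlation, an assumed missingness model, normal differences, and Day 14 pairs being available for subjects without Day 30. The documents give none of these.

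**What to change.** Before database lock, add one analysis to SAP 10.3.2.2: a likelihood-based repeated-measures model of the reviewer's patency grade, with side, visit (Day 14, Day 30) and side-by-visit as fixed effects and an unstructured within-subject covariance over the four side-visit grades. Run it regardless of the 10% trigger. Report the Day 30 treatment-minus-control contrast with its 95% CI beside the paired t-test, which stays primary. The model also keeps a single readable Day 30 side.

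Timing matters, because SAP 9.2 treats analyses designed after database lock as post hoc and exploratory.

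The cost is a paragraph of SAP text and one model; no visit, data item, sample size or decision rule changes. The drawback is reliance on missing-at-random and on the Day 14 to Day 30 relation, which nasal steroid sprays or rescue after Day 14 may disturb. The existing tipping-point analysis probes departures from that assumption and should be kept.
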